Figure 2. Enrollment, assignment to treatment with or without randomization of 48 study patients with PCT in the interim analysis, and inclusion of the 30 patients who achieved a normal plasma porphyrin concentration in the analysis comparing time to remission with phlebotomy and low-dose hydroxychloroquine.

porphyrin level may not be a sign of full remission. Therefore, continuing treatment with

hydroxychloroquine until these additional outcome measures become normal may be beneficial. There were no significant side effects with either treatment. Follow up was insufficient to compare recurrence rates with these treatments.

Based on these interim findings we concluded that (1) the study should continue with changes to better assess response and durability with these two standard treatments. (2) Time to achieving treatment endpoints in addition to normal plasma porphyrin levels should be assessed. (3) All available PCT patients who require treatment should be enrolled, if possible, and assigned treatment based on medical indications, preference, or randomization (for patients suitable for either treatment). (4) A noninferiority design is not appropriate, because most subjects are not randomized, and outcomes should be compared using descriptive methods. (5) Power analyses to assess effects of clinical features and susceptibility factors should emphasize those of greatest clinical interest. We consider that age and sex are the clinical features of greatest interest, and alcohol use, hepatitis C and UROD mutations are susceptibility factors of greatest interest. (6) Longer follow up is needed to assess durability of treatment, and whether this relates to susceptibility factors. (7) The single primary outcome was evaluable in ~2/3 of patients in the interim analysis. Inclusion of additional outcomes is likely to provide evaluable outcomes for a greater proportion of patients. (8) This study also will provide serial data and samples on a cohort of PCT participants in whom treatment responses and complete remission are rigorously documented, which will be valuable for future cross sectional and longitudinal research on the pathogenesis and natural history of this disease.

3. Specific aims

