Liver ultrasound and biopsy will be recommended to participants based on clinical indications per the investigator, these tests will not be done solely for the study. If completed at an outside institution records will be obtained. Tissue will be examined microscopically, and iron content will be measured if possible. Evaluation of liver histology is not required for this study because the results are usually not essential for diagnosis or classification of PCT participants, identifying risk factors, or deciding on treatment options. However, liver biopsy is the best means of assessing liver iron concentration, and is often recommended for assessing the degree of pretreatment damage to the liver associated with hepatitis C, alcohol, steatosis, etc. Results of liver biopsy, when available, will be recorded on the CRFs and tabulated and analyzed with other clinical information that pertains to PCT.

Treatment assignment. Before assigning treatment, subjects will be evaluated for the contraindications to treatment with hydroxychloroquine and phlebotomy listed in Table 3 and 4.

If one of these treatments is contraindicated, the reason(s) will be recorded, and the subject will be assigned to the other treatment. Participants eligible for both will be assigned by randomization.

Table 3. Contraindications to treatment with hydroxychloroquine.

- 1. Unwillingness to consider this form of treatment
- 2. Lactating women
- 3. Psoriasis
- 4. Significant retinal disease
- 5. Glucose-6-phosphate dehydrogenase deficiency
- Recent and continued heavy use of alcohol (defined as 28 or more drinks per week)
- 7. Recent and continued use of hepatotoxic drugs such as acetaminophen, isoniazid or valproic acid
- Marked abnormalities in liver function tests at baseline, such as serum bilirubin >3mg/dL, serum alanine aminotransferase >200 U/L, or prothrombin time >16 seconds (or INR >1.4)
- 9. Advanced renal disease, with serum creatinine >3 mg/dL
- 10. Poor tolerance or poor response to this treatment in the past
- 11. HFE genotypes C282Y/C282Y or C282Y/H63D and serum ferritin above the normal range (>336 ng/mL)
- 12. Substantial iron overload, with serum ferritin >500 ng/mL, in the absence of these *HFE* genotypes
- 13. Marked iron overload (3+ or 4+) on liver biopsy, if available

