4.R. Data analysis and statistical considerations. This was originally designed as a randomized noninferiority clinical trial, with inclusion of participants who could not be randomized in a substudy, but with the same treatment and follow up for all participants. We had anticipated that 90% of participants could be randomized, and the intent was to include only randomized participants in the noninferiority analysis. A planned interim analysis, which has been published (45) found that more than half the participants could not be randomized due to medical reasons or patient preference; therefore the interim data was analyzed for the randomized participants and for all participants. Although the treatments appeared equivalent in terms of time to remission, statistical significance was not achieved. Therefore, after formation of the Porphyrias Consortium (PC), the study was continued as a PC study with the goal of enrolling enough participants for a statistically significant result. Based on the interim analysis, the PC investigators identified additional value in continuing this study to enroll a larger number of participants. 1.) Like the PC Longitudinal Study (LS), PC7201, this study enrolls participants with well documented PCT who are characterized for all of the known susceptibility factors. which are multiple but different for individual participants. But unlike the LS, this study carefully documents treatment response and remission, and allows assessment of treatment response and durability as related to specific, multiple susceptibility factors, some of which may change over time. 2.) This study will allow examination of the importance of newly-identified or postulated susceptibility factors, not only for contributing to development of PCT but for affecting treatment responses. 3.) This study is developing for the first time reference information on time to remission for phlebotomy, presently for comparison with hydroxychloroguine. But additional treatment arms may be added to the study as new therapeutic approaches are developed in the future.

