The study will continue as a more pragmatic study relevant to clinical practice, with assignment to treatment based on uniform criteria and randomization only of participants eligible for both treatments, to avoid unnecessary bias. Therefore, it will be a two-group study with no substudy. A descriptive approach to data analysis will be employed, with clinically relevant comparisons of the two treatments, rather than a noninferiority analysis.

Inclusion of all available participants rather than just the minority that can be randomized has a number of advantages. Participants eligible for both treatments (and therefore eligible for randomization) might respond differently than those who are not, since some of the reasons that make participants ineligible for one treatment relate to certain susceptibility factors and to prior treatment experience. Exclusion of a majority of participants from treatment comparisons also would make the study less pragmatic and less clinically relevant. In the interim analysis, randomized and nonrandomized participants did not differ in terms of clinical and demographic

features, but such important comparisons would be more meaningful with a larger number of participants. In the amended study, participants who are eligible for both treatments are to be randomized as a method for choosing between treatments that is needed in the study to avoid bias, but not as a study design feature. Bias might arise, for example, from existing site-specific treatment preferences.

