A total of at least 100 participants will be assigned, based on medical criteria, preference, or (if eligible for both treatments) by randomization, to one of these standard treatment groups. CRFs will be completed for each patient, including porphyrin levels, and data entered into the study database. This database is designed by and housed at the Data Management and Coordinating Center (DMCC) at the University of South Florida in Tampa. The DMCC is supported by the NIH Rare Diseases Clinical Research Network and serves as the secure repository for de-identified data for all consortia in the Network. Upon approval from the UTMB IRB and the Porphyrias Consortium DSMB, data from patients previously enrolled in this study at UTMB starting in 2006 before the study was a RDCRN study will be entered into the database. Subjects will be contacted to give their consent for this data transfer to the DMCC and storage in a federal data repository. For subjects who are now deceased consent will be obtained from next of kin. For subjects who cannot be re-contacted or where the next of kin cannot be re-contacted, approval of the UTMB IRB and the Porphyrias Consortium DSMB will be sought for this data transfer. Transferring this previously collected de-identified data is not expected to cause any increased risks to subjects. Data will be verified and edited where necessary for completeness and consistency by comparison with source documents. Study outcomes, such as time to achieving biochemical endpoints, will be determined from this data. As was found in the interim analysis, assignment to the two groups is unlikely to be equal, and more will be assigned to phlebotomy than to hydroxychloroquine. As in the interim analysis, times to achieving measures of remission are not expected to be substantially different for the two treatment groups. Effects of multiple susceptibility factors and other clinical and demographic features on treatment response and durability will be further examined. Outcome measures such as time to remission will be compared using Cox proportional models to study the effects of susceptibility factors on the hazard ratio to compare the two treatments. All patients who start treatment will be included in the analysis. Safety measures will be compared more descriptively where the adverse effects of each type of treatment are different.

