The following susceptibility factors for PCT will be summarized and tabulated, and examined for balance across treatment groups. Differences in response based on susceptibility factors will be examined by multivariate analysis. The following susceptibility factors will be emphasized in this analysis:

- 1. Alcohol use (presence or absence)
- 2. Smoking (presence or absence)
- 3. Estrogen use (presence or absence)
- 4. Hepatitis C (presence or absence)
- 5. HIV (presence or absence)
- 6. UROD mutations (presence or absence)
- 7. HFE mutations (presence or absence of C282Y and H63D, and specific genotype combinations)

The analysis regarding susceptibility factors will take into consideration that some (e.g. homozygotes for HFE mutations with high ferritin levels) are medical reasons for assignment to one treatment group and not the other. We recognize that because the number of participants in subgroups based on susceptibility factors or combinations of susceptibility factors will be

relatively small, and it may not be possible to detect or exclude statistically significant differences for all susceptibility factors. The data is expected to support continuing this study with larger numbers of participants, or to suggest whether other studies should be designed to clarify the effects of these factors on treatment response and durability.

Additional modeling will assess factors affecting the frequency of recurrence and seasonality effects using logistic regression modeling and log-rank testing, respectively.

Sample Size and Power. A sample size calculation was performed to assess power for a study assessing the effect of factors on time to remission. Extremely common or rare factors are detected with 80% power for 90 subjects (and some dropout) when the hazard ratios are 2.3 (alcohol consumption and UROD deficiency), 2.2 (smoking history), 3.2 (estrogen usage), 2.0 (hepatitis C), and 1.9 (HFE mutations). In summary, this approach for times to remission leads to a sample size of approximately 50 subjects per group. All analyses were conducted in nQuery Advisor Version 5.0 (Janet Elashoff (2002); nQuery Advisor Version 5.0 User's Guide. Los Angeles, CA).

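### Baseline ferritin partly decides treatment assignment in this study, but Section 4.R neither adjusts for it, tabulates it for balance, nor gives a treatment hazard ratio below the ferritin/HFE cut-offs

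*Combined protocol and SAP*

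**What the plan says.** **Assignment.** Section 4.E, Treatment assignment: "If one of these treatments is contraindicated, the reason(s) will be recorded, and the subject will be assigned to the other treatment". Table 3 lists as contraindications to hydroxychloroquine a ferritin above 500 ng/mL, and a ferritin above 336 ng/mL with genotype C282Y/C282Y or C282Y/H63D. Participants eligible for both treatments are randomised, and unwillingness to have one treatment counts as a contraindication to it.

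**Analysis.** Section 4.R: outcomes are "compared using Cox proportional models to study the effects of susceptibility factors on the hazard ratio to compare the two treatments", and "All patients who start treatment will be included in the analysis". Seven susceptibility factors (alcohol, smoking, estrogen, hepatitis C, HIV, UROD and HFE mutations) are to be tabulated, "examined for balance across treatment groups" and emphasised in a multivariate analysis. Ferritin is not among them. The section recognises that some factors, with HFE homozygotes who have high ferritin as its example, "are medical reasons for assignment to one treatment group and not the other". It does not say how the analysis will allow for this.

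**Pooling.** This is deliberate. Section 2 concludes that noninferiority is not appropriate "because most subjects are not randomized, and outcomes should be compared using descriptive methods". Section 4.R adds that "Participants eligible for both treatments (and therefore eligible for randomization) might respond differently than those who are not". At the interim the reverse precaution was taken: "therefore the interim data was analyzed for the randomized participants and for all participants". The current plan does not carry the randomised-only comparison forward.

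**The concern.** A baseline variable that steers patients to one arm and also affects the outcome confounds the comparison of arms. Ferritin meets the first condition by rule. For the second, Section 2 (treatment by phlebotomy), 4.C and 4.H all link higher starting ferritin or marked iron overload to more phlebotomies or a longer course. Section 4.F places the ferritin target before porphyrins normalise. Later remission in high-ferritin patients is an inference from these statements; the protocol does not report it as a finding.

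If the inference is right, slower-remitting patients are concentrated in the phlebotomy arm and hydroxychloroquine looks faster than it is. The working hypothesis is that hydroxychloroquine is comparable in time to remission, so this bias would favour the hypothesis. Section 1.B says that the results are meant to guide the choice between the treatments, so a descriptive hazard ratio will still be read as evidence.

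**Working it through.** **1. The plan's own figure.** There is none to reproduce. The power paragraph of 4.R covers susceptibility factors (hazard ratios 1.9 to 3.2) and gives no power or precision for the treatment hazard ratio.

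**2. Inputs.** From the documents: interim median 6 to 7 months (6.5 used); 17 phlebotomy and 13 hydroxychloroquine patients among the 30 evaluable of 48; phlebotomies about every 2 weeks; usually about 6 to 8 needed. Assumed: share *f* of phlebotomy patients above the cut-offs, 0.2 to 0.5 (*f* × 17/30 = 11% to 28% of all participants); average extra phlebotomies *k* in them, 2 to 8; exponential times; no true treatment difference. A hazard ratio above 1 means faster remission on hydroxychloroquine.

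**3. Bias of the unadjusted hazard ratio.** One extra phlebotomy adds 14/30.44 = 0.46 month. The relative remission hazard above the cut-offs is *h* = 6.5/(6.5 + 0.46*k*), and the apparent hazard ratio is approximately 1/(1 − *f* + *f* × *h*).

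| *k* | *h* | *f* = 0.2 | *f* = 0.5 |
|---|---|---|---|
| 2 | 0.88 | 1.03 | 1.07 |
| 4 | 0.78 | 1.05 | 1.12 |
| 8 | 0.64 | 1.08 | 1.22 |

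Simulated Cox models with log-normal ferritin, and a delay that starts at zero at 500 ng/mL and rises above it, gave 1.03 to 1.07 for an average *k* of 2 and 1.04 to 1.22 for an average of 4 to 8.

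**4. Scale at n=100.** If the interim evaluable fraction holds, events are 100 × 30/48, about 62. The standard error of the log hazard ratio is 1/√(62 × 17/30 × 13/30) = 0.256. Then ln(1.03)/0.256 = 0.1 and ln(1.2)/0.256 = 0.7 standard errors. The 95% interval around 1 is about 0.61 to 1.65 by formula (0.60 to 1.67 simulated).

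**5. Does the named HFE factor deal with it?** Only slightly. It does not identify patients with ferritin above 500 ng/mL who lack the two listed genotypes. In simulation, a two-mutation HFE term (14% prevalence, as in Table 2) moved a biased hazard ratio from 1.14 to 1.12, and in a second scenario from 1.19 to 1.16. Log ferritin brought these to 1.04 to 1.05, and restriction below the cut-offs to about 0.97 to 1.00.

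**6. Opposite direction.** Table 4 sends some patients (for example, marrow dysfunction or poor past response to phlebotomy) to hydroxychloroquine. If they are 10% to 20% of that arm with relative hazard 0.8 to 0.6 (assumed), the apparent hazard ratio is multiplied by 1 − 0.1 + 0.1 × 0.8 = 0.98, down to 1 − 0.2 + 0.2 × 0.6 = 0.92.

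**The case against.** The best case for the plan has four parts.

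- **The problem is recognised.** Section 4.R names high ferritin with HFE mutations as a reason for assignment, puts HFE genotype in the multivariate analysis, and says that other clinical and demographic features will be examined. This stands as recognition. It names no covariate, stratum or restriction, and step 5 shows that HFE genotype is a weak substitute for ferritin.
- **Pooling is a reasoned choice.** Most patients cannot be randomised, and the comparison is descriptive. This stands too. A reader might infer that the pooled comparison is invalid or should give way to randomised patients only. The documents do not support that: they give a pragmatic reason for including everyone, and a randomised-only estimate would be imprecise.
- **The interim showed no difference.** Medians were 6 to 7 months for both treatments in all 30 evaluable and in the 17 randomised patients, and Section 4 reports similar responses in randomised and nonrandomised participants. This is mildly reassuring. The 95% interval around a hazard ratio of 1 is about 0.49 to 2.06 with 30 events and 0.39 to 2.59 with 17 (equal split assumed), so it cannot exclude a bias of this size.
- **The larger figures fit the protocol poorly.** With *f* = 0.5 and *k* = 4 to 8, the implied phlebotomy median is 7.3 to 8.1 months, above the reported 6 to 7. Eight extra phlebotomies at least double the usual course. With 17 phlebotomy patients this does not refute the upper end, but it favours the lower. Biases of 1.5 can be produced with steeper hazards, but the documents give no support for them.

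**Conclusion.** The point holds as a gap in the specified analysis. The current rules send patients above the ferritin/HFE cut-offs to phlebotomy only, the protocol itself gives reason to expect a slower course in them, and 4.R neither adjusts for ferritin nor tabulates it. The hazard ratio may be biased, plausibly towards hydroxychloroquine. Under the assumptions above, a true value of 1 would appear as about 1.03 to 1.2, usually less than one standard error at n=100. The share above the cut-offs and the delay are assumed, and patients sent to hydroxychloroquine under Table 4 could offset part of the bias, so neither size nor direction is certain.

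A reader might also infer that no hydroxychloroquine patient lies above the cut-offs. That follows from the current rules, but 52 patients were enrolled at one site before the study became a consortium protocol, and the documents do not give the thresholds then in force. This should be checked in the data. The plan should be changed on this point, but the gap does not invalidate the study.

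**What to change.** In Section 4.R, keep the all-participant comparison and add baseline ferritin to the balance table. Report beside the pooled result:

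- **(a)** a treatment hazard ratio from a Cox model with treatment and log baseline ferritin, kept separate from the seven-factor susceptibility model. At 62 events this leaves 62/2 = 31 events per parameter, against 62/9 = 6.9 if treatment, ferritin and seven factors share one model.
- **(b)** a treatment hazard ratio restricted to participants with ferritin at or below 500 ng/mL (at or below 336 ng/mL with C282Y/C282Y or C282Y/H63D). Under the current rules, adjustment above these limits is extrapolation. State whether any early enrollee above them received hydroxychloroquine.

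Two further analyses may be added as descriptive sensitivity analyses, with their imprecision stated. One also excludes participants with other recorded contraindications. These are not fully ascertainable: eye evaluation is scheduled only for hydroxychloroquine participants, and biopsy counts only if available. The other is a randomised-only hazard ratio: at an assumed 62 × 17/30 = 35 events, its interval around 1 is about 0.52 to 1.94.

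**Cost.** Plan wording and a little more analysis. The Schedule of Events already has ferritin and HFE testing at baseline for every participant; that early enrollees' baseline ferritin is on file is an assumption. Simulated 95% intervals around 1 widen from 0.60–1.67 to between 0.59–1.70 and 0.56–1.79 for (a), and to between 0.58–1.73 (55 events) and 0.53–1.87 (44 events) for (b). Preference-assigned patients in (b) remain unrandomised.
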